4.2 Registration of Patients

This study is supported by the NCI Cancer Trials Support Unit (CTSU).

Prior to the recruitment of a patient for this study, investigators must be registered members of a Cooperative Group. Each investigator must have an NCI investigator number and must maintain an "active" investigator registration status through the annual submission of a complete investigator registration packet (FDA Form 1572 with original signature, current CV, Supplemental Investigator Data Form with signature, and Financial Disclosure Form with original signature) to the Pharmaceutical Management Branch, CTEP, DCTD, NCI. These forms are available on the CTSU Web site (enter credentials at <https://www.ctsu.org>; then click on the Register tab) or by calling the PMB at [contact] Monday through Friday between 8:30 a.m. and 4:30 p.m. Eastern time.

Each investigator or group of investigators at a clinical site must obtain IRB approval for this protocol and submit IRB approval and supporting documentation to the CTSU Regulatory Office before they can enroll patients. Study centers can check the status of their registration packets by querying the Regulatory Support System (RSS) site registration status page of the CTSU member web site by entering credentials at <https://www.ctsu.org>.

Submitting Regulatory Documents

Once your site is authorized to begin the IRB approval process, please apply to the CIRB for participation approval and follow local IRB submission requirements as outlined by your institution. If local IRBs have questions or concerns regarding the intervention, they are instructed to contact ECOG-ACRIN or the study team directly. Once approval is received, you may move forward with study initiation if you are randomized to Arm A (control). If you are randomized to Arm B (intervention), you are required to submit all intervention materials (addendum I) to your IRB, if you have not already done so, for the next phase of approval before moving forward with study initiation.

Before an Institution may enter patients, protocol specific documents must be submitted to the CTSU Regulatory Office. Submit required forms and documents to the CTSU Regulatory Office via the Regulatory Submission Portal on the CTSU website.

To access the Regulatory Submission Portal log on to the CTSU members' website → Regulatory → Regulatory Submission

Institutions with patients waiting that are unable to use the Regulatory Submission Portal should alert the CTSU Regulatory Office immediately at [name] in order to receive further instruction and support.

Rev. 11/17
Rev. Add8

Checking Your Site's Registration Status:

Site registration status may be verified on the CTSU members' website.

- Click on the *Regulatory* at the top of the screen;
- Click on the *Site Registration*; and
- Enter the sites 5-character CTEP Institution Code and click on Go
- Additional filters are available to sort by Protocol, Registration Status, Protocol Status, and/or IRB Type

NOTE: The status shown only reflects institutional compliance with site registration requirements as outlined within the protocol. It does not reflect compliance with protocol requirements for individuals participating on the protocol or the enrolling investigator's status with NCI or their affiliated networks.

Downloading Site Registration Documents:

Download the site registration forms from the protocol-specific page located on the CTSU members' website. Permission to view and download this protocol and its supporting documents is restricted based on person and site roster assignment. To participate, the institution and its associated investigators and staff must be associated with the LPO or a PO on the protocol.

- Log on to the CTSU members' website <https://www.ctsu.org> using your CTEP-IAM username and password
- Click on the Protocols in the upper left of your screen
- Either enter the protocol # in the search field at the top of the protocol tree, or
- Click on the By Lead Organization folder to expand
- Click on the ECOG-ACRIN link to expand, then select trial protocol #E1Q11
- Click on Documents, select the Site Registration, and download and complete the forms provided.

NOTE: For sites under the CIRB initiative, IRB data will load automatically to the CTSU as described above.)

Required Protocol Specific Regulatory Documents

Rev. 11/17

1. Copy of IRB Informed Consent Document.

NOTE: Any deletion or substantive modification of information concerning risks or alternative procedures contained in the sample informed consent document must be justified in writing by the investigator and approved by the IRB.

2. A. CTSU IRB Certification Form.
Or
B. Signed HHS OMB No. 0990-0263 (replaces Form 310).
Or
C. IRB Approval Letter

NOTE: The above submissions must include the following details:

- Indicate all sites approved for the protocol under an assurance number.
- OHRP assurance number of reviewing IRB
- Full protocol title and number
- Version Date
- Type of review (full board vs. expedited)
- Date of review
- Signature of IRB official

4. E1Q11 Study Participation Interest and Feasibility Form (See Section 4.7.4)
5. Site Signature Log and Delegation of Responsibilities (ECOG-ACRIN website)
6. Site Training Record (ECOG-ACRIN website)-**Required only for Arm B sites**
7. Site Referral Network Form (ECOG-ACRIN website) – **Required only for Arm B sites**

Patients must not start protocol prior to registration.

Patient registration can occur only after eligibility criteria have been met, and the study site is listed as 'approved' in the CTSU RSS. Patients must have signed and dated all applicable consents and authorization forms.

The Oncology Patient Enrollment Network (OPEN) is a web-based registration system available on a 24/7 basis. OPEN is integrated with CTSU regulatory and roster data and with the Lead Protocol Organization (LPOs) registration/randomization systems or Theradex Interactive Web Response System (IWRS) for retrieval of patient registration/randomization assignment. OPEN will populate the patient enrollment data in NCI's clinical data management system, Medidata Rave.

Requirements for OPEN access:

- A valid CTEP-IAM account;
- To perform enrollments or request slot reservations: Be on a LPO roster, ETCTN Corresponding roster, or PO roster with the role of Registrar. Registrars must hold a minimum of an AP registration type;
- Have an approved site registration for a protocol prior to patient enrollment.

To assign an Investigator (IVR) or Non-Physician Investigator (NPIVR) as the treating, crediting, consenting, drug shipment (IVR only), or receiving investigator for a patient transfer in OPEN, the IVR or NPIVR must list the IRB number used on the site's IRB approval on their Form FDA 1572 in RCR.

Prior to accessing OPEN site staff should verify the following:

- All eligibility criteria have been met within the protocol stated timeframes.

- All patients have signed an appropriate consent form and HIPAA authorization form (if applicable).

Access requirements for OPEN:

- Site staff will need to be registered with CTEP and have a valid and active CTEP-IAM account and a 'Registrar' role on either the LPO or participating organization roster. This is the same account (user id and password) used for the CTSU members' web site.
- To perform registrations, the site user must have been assigned the 'Registrar' role on the relevant Group or CTSU roster and hold a minimum of an AP registration type.
- To perform registrations on protocols for which you are a member of the Lead Group, you must have an equivalent 'Registrar' role and hold an account of AP or higher on the Lead Group roster. Role assignments are handled through the Groups in which you are a member
- To perform registrations to trials accessed via the CTSU mechanism (i.e., non-Lead Group registrations) you must have the role of Registrar on the CTSU roster and hold a minimum of an AP registration type.

NOTE: The OPEN system will provide the site with a printable confirmation of registration. Please print this confirmation for your records.

Access OPEN at <https://open.ctsu.org> or from the OPEN link on the CTSU members' website. Further instructional information is provided on the OPEN tab of the CTSU members' side of the CTSU website at <https://www.ctsu.org> or at <https://open.ctsu.org>. For any additional questions contact the CTSU Help Desk at [name] or [contact].

The following information will be requested

4.3 Protocol Number

4.4 Investigator Identification

4.4.1 Institution and affiliate name (Institution CTEP ID)

4.4.2 Investigator's name (NCI number)

4.4.3 Cooperative Group Credit

4.4.4 Credit Investigator

4.4.5 Protocol specific contact information

4.5 Patient Identification

4.5.1 Patient's initials (first and last)

4.5.2 Patient's Hospital ID and/or Social Security number

4.5.3 Patient demographics

4.5.3.1 Gender

4.5.3.2 Birth date

4.5.3.3 Race

4.5.3.4 Ethnicity

- 4.5.3.5 Nine-digit ZIP code
- 4.5.3.6 Method of payment
- 4.5.3.7 Country of residence

Rev. Add8 4.6 Eligibility Verification

- 4.6.1 Patients must meet all of the eligibility requirements listed in Section [3](#).

Rev. Add9 4.7 COG Patient Registration Enrollment Information

For COG Credited Enrollments ONLY: Prior to enrollment on this study, patients enrolling must be assigned a COG patient ID number. This number is obtained via the Patient Registry module in OPEN once authorization for the release of protected health information (PHI) has been obtained. The COG patient ID number is used to identify the patient in all future interactions with COG. If you have problems with the registration, please refer to the online help. For additional help or information, please contact the CTSU Help Desk at [name] or [contact]. See [Appendix IV](#) for the Information Sheet for teens from 15 through 17 years of age.

4.8 Additional Requirements

- 4.8.1 Patients and clinicians must provide a signed and dated, written informed consent form.

NOTE: Copies of the consent are not collected by the ECOG-ACRIN Operations Office -Boston.

- 4.8.2 Blood samples for the endocrine markers should be submitted as outlined in Section [9](#) per patient consent.

NOTE: ECOG-ACRIN requires that biological samples submitted from patients participating in E1Q11 be entered and tracked via the online ECOG Sample Tracking System (STS). See Section [9.5](#).

NOTE: Institutions must complete and submit the Quest Diagnostics Sub-Account Information Sheet ([Appendix III](#)) to create their study-specific account number in order to obtain supplies and arrange for courier service for the blood sample collections.

4.8.3 Medidata Rave

Medidata Rave is a clinical data management system being used for data collection for this trial/study. Access to the trial in Rave is controlled through the CTEP-IAM system and role assignments.

Requirements to access Rave via iMedidata:

- A valid CTEP-IAM account; and
- Assigned a Rave role on the LPO or PO roster at the enrolling site of: Rave CRA, Rave Read Only, Rave CRA (LabAdmin), Rave SLA, or Rave Investigator.

- Rave role requirements:
 - Rave CRA or Rave CRA (Lab Admin) role must have a minimum of an Associate Plus (AP) registration type;
 - Rave Investigator role must be registered as an Non-Physician Investigator (NPIVR) or Investigator (IVR); and
 - Rave Read Only role must have at a minimum an Associates (A) registration type.

Refer to

<https://ctep.cancer.gov/investigatorResources/default.htm> for registration types and documentation required.

Upon initial site registration approval for the study in RSS, all persons with Rave roles assigned on the appropriate roster will be sent study invitation e-mail from iMedidata. To accept the invitation, site users must log into the Select Login (<https://login.imedidata.com/selectlogin>) using their CTEP-IAM user name and password, and click on the “accept” link in the upper right-corner of the iMedidata page. Please note, site users will not be able to access the study in Rave until all required Medidata and study specific trainings are completed.

Trainings will be in the form of electronic learnings (eLearnings), and can be accessed by clicking on the link in the upper right pane of the iMedidata screen. If an eLearning is required and has not yet been taken, the link to the eLearning will appear under the study name in iMedidata instead of the Rave EDC link; once the successful completion of the eLearning has been recorded, access to the study in Rave will be granted, and a Rave EDC link will display under the study name.

Users that have not previously activated their iMedidata/Rave accounts will also receive a separate invitation from iMedidata to activate their account. Account activation instructions are located on the CTSU website, Rave tab under the Rave resource materials (Medidata Account Activation and Study Invitation Acceptance). Additional information on iMedidata/Rave is available on the CTSU website under the Rave tab at <http://www.ctsu.org/RAVE/> or by contacting the CTSU Help Desk at [name] or by e-mail at [contact].

Provider data collection will be done in the PROMIS Assessment Center, a web-based application.

4.8.4 Site Credentialing

Sites interested in participating in E1Q11 must have an active CTEP ID number. Site staff who do not have a CTEP ID number must first register with the Pharmaceutical Management Branch (PMB, CTEP) at <https://eapps-ctep.nci.nih.gov/iam/>. For additional information on obtaining a CTEP ID number and joining ECOG, go to <http://ecog-acrin.org/about-us/membership/how-to-join>. If you have any questions, please contact [contact].

To express interest in participating, sites must email [contact] with the following information:

First and Last Name of the Primary Contact at your Institution
Email address for Primary Contact
Site Name
CTEP Site ID
Street Address
City, State, Zip

NOTE: The person identified as the Primary Contact will be the person responsible for data entry in Rave.

The Primary Contact will receive an email letting them know their site has been registered in Rave and that they can access the “E1Q11 Study Participation and Feasibility” study to complete the Study Participation and Feasibility Interest Form in Medidata Rave. (Please note that only the Primary Contact at each NCORP group will need to complete the E1Q11 Study Participant and Feasibility Interest Form. It will not be necessary for each affiliate to complete the form.)

Rev. 11/16

Rev. Add11

4.8.5 Data Quality Portal

The Data Quality Portal (DQP) provides a central location for site staff to manage unanswered queries and form delinquencies, monitor data quality and timeliness, generate reports, and review metrics.

The DQP is located on the CTSU members’ website under Data Management. The Rave Home section displays a table providing summary counts of Total Delinquencies and Total Queries. DQP Queries, DQP Delinquent Forms and the DQP Reports modules are available to access details and reports of unanswered queries, delinquent forms, and timeliness reports. Review the DQP modules on a regular basis to manage specified queries and delinquent forms.

The DQP is accessible by site staff that are rostered to a site and have access to the CTSU website. Staff that have Rave study access can access the Rave study data using a direct link on the DQP.

To learn more about DQP use and access, click on the Help icon displayed on the Rave Home, DQP Queries, and DQP Delinquent Forms modules.

NOTE: Some Rave protocols may not have delinquent form details or reports specified on the DQP. A protocol must have the Calendar functionality implemented in Rave by the Lead Protocol Organization (LPO) for delinquent form details and reports to be available on the DQP. Site staff should contact the LPO Data Manager for their protocol regarding questions about Rave Calendaring functionality.

5. Methodology

Rev. 11/16

5.1 Randomization

Participating sites will be randomized to standard practice (Arm A) or intervention (Arm B). Due to logistical challenges of having both intervention and non-intervention programs within a single institution, the unit of randomization will be the institution (i.e., a cluster randomized approach) rather than individual patient. Institutions (i.e., the NCORP groups) participating in the study will be randomized to one of the two arms: Arm A without intervention and Arm B with intervention. Upon registration to this study, patients will be assigned to a study arm depending on the institutional assignment. Training for those randomized to Arm B will be offered at ECOG-ACRIN Group meetings and/or through a webinar on the ECOG website to enhance feasibility of site participation. Trainings specific to the intervention will be provided only to Arm B sites.

5.2 Study Arms and Intervention

5.2.1 Arm A – Non-intervention

Sites randomized to non-intervention will function with usual standard practice related to reproductive health.

5.2.2 Arm B – Intervention

Sites randomized to the intervention will receive training and intervention materials. Information specific to the intervention can be found in Addendum I.

5.3 Provider Survey Administration Instructions - Using Assessment Center™

5.3.1 Electronic administration of the Provider Surveys will be done using the study's website in the PROMIS Assessment Center.

<http://www.assessmentcenter.net/ac1/Assessments/E1Q11>.

5.3.2 Prior to accessing the website, each provider will need to know his/her own physician's CTEP ID and site name/site CTEP ID.

5.3.3 User-friendly instructions will then be shown on the screen.

5.3.4 For providers who complete assessments using the Assessment Center, sites will log completion of these assessments in Medidata Rave. If the provider needed assistance or was unable to complete assessments at a given timepoint, the reason or type of assistance should be provided.

5.3.5 For sites with troubleshooting inquiries regarding the use of Assessment Center, the following steps should be followed: 1) All sites should direct troubleshooting inquiries directly to the E1Q11 Data Associate; 2) ECOG-ACRIN will forward unresolved inquiries to Northwestern University research staff; 3) Research staff at Northwestern University may forward unresolved inquiries to Assessment Center for final resolution. NOTE: Assessment Center should not receive any troubleshooting inquiries directly from sites.

Rev. 11/17

5.4 Patient Recruitment

Patients from oncology clinics with newly diagnosed cancer are possible candidates for the study. Complete eligibility criteria are included in Section [3](#). After the diagnosis of cancer is given to the patient, the primary provider will refer the patient to the study personnel for initial contact. The primary provider is defined as the clinician (MD, nurse practitioner, PA-C) that is clinically assessing the oncology patient. Subjects must enroll prior to initiation of chemotherapy or radiation, if applicable.

Institutions will identify a clinical research nurse (CRN)/CRA that will be responsible for all aspects of this study. The designated (CRN)/CRA from each institution will be available to work with physicians during the clinical session to identify and recruit patients. This person will discuss the details of this study with appropriate care and thoughtfulness as she has recently received the diagnosis of a cancer. If the patient agrees, she will be screened for study eligibility at that time or at a subsequent visit as deemed appropriate by study personnel. This person will also be available to answer any questions regarding the study.

Patients will either be enrolled in the study or listed on the “Patient Log” ([Appendix II](#)), which requires a reason for the patient’s decision not to participate. Please keep a copy of the Patient Log in patient chart at institution.

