4.1 Selection and Randomization of Sites

To ensure patient diversity in this study, all Minority/Underserved National Cancer Institute Community Oncology Research Programs (MU NCORP) sites will be invited to participate. The remainder of sites will be filled by NCORPs.

All MU NCORPs and selected NCORPs will receive an invitation letter from the Group Chair together with the study chair including a brief description of the study. Potential sites will be asked to respond to several questions related to site

characteristics, including patient volume and possible accrual and reproductive-related services available in the areas of each site, to determine feasibility of utilizing the site for trial recruitment and the site's level of interest in serving as a study site. Information from sites that respond will be reviewed by the study chair and the study team. Sites that express interest in participating and that report adequate patient volume to meet the protocol accrual goal will be sent a formal invitation to participate in this study. Depending on the number of participating MU NCORPs, other NCORPs will be randomly selected to participate in this study. Once sites have been selected, they will be randomized to the intervention or non-intervention arm. Sites randomized to the intervention arm will receive access to additional materials and information specific to the intervention including the intervention content.

A notice of randomized intervention assignment will be forwarded by the ECOG-ACRIN Operations Office - Boston. Each participating institution will be sent a notice confirming the assignment of the intervention or non-intervention arm.

Rev. 11/17

Rev. Add8

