5.5 Data Collection

Patients will be followed over time and all surveys will be administered as described in Table 1 (Section [7](#)).

Rev. 11/16

- 5.5.1 Following site randomization and local IRB approval, a consent form will be given to each provider (oncology staff, i.e. MD, nurse practitioner or PA-C, that clinically assesses the patient). A signed provider consent form is required for participation.
- 5.5.2 Upon site study activation a delegation of responsibility log should be completed and submitted to CTSU prior to enrolling the first patient
- 5.5.3 Patients will be recruited to participate at their scheduled provider appointment. Study staff will approach patients who are possible candidates to determine interest. If interested, eligibility will be confirmed (Section [3](#)).

Rev. 11/17

- 5.5.4 A consent form will be given to interested and eligible patients. The consent form should be completed on the same day eligibility is confirmed, however, it must be signed prior to treatment initiation (See Section [7](#) Patient-specific timeline).
- 5.5.5 Patient will have the baseline provider visit, complete baseline surveys and be registered to the trial on the same day of consent. If this is not feasible, then all baseline requirements (including registration) must be completed within one week of patient consent. Baseline provider visits, completion of baseline surveys and study registration must be completed on same day. (Table 1).
- 5.5.6 The designated research staff person (CRN or CRA) from each institution will administer questionnaires and assist with the completion of form(s) at the baseline and follow-up visits, as necessary. A CRN or CRA must review form(s) for completeness as

soon as the patient finishes them to ensure all items have been marked appropriately.

- 5.5.7 The scheduled study tools must be completed during the visit.
- 5.5.8 Completed clinician and patient form(s) will be entered into Medidata Rave within 7 days of collection.

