5.7.2 Patient Reported Outcomes Assessment Schedule

If a patient is eligible to participate in this study and the physician approves, the study is further discussed with the patient. Patients providing consent will be registered on trial. Participants will complete a total of 8 assessment visits (including baseline). Structured interviews will be administered to participants at the timepoints listed below. At each time point, two questionnaires will be administered by a study team member. Completion of these forms on a given visit should take about 10-20 minutes. Patient interviews are designed to assess the patient's reproductive health history, management and goals at baseline and as they progress through cancer treatment. Additionally, the Sexual Function Survey, which includes the PROMIS Sexual Function Brief Profile v1.0 – Female, is designed to assess sexual health at diagnosis and throughout treatment.

Patients will be assessed according to the following schedule:

Rev. Add8

Patient Baseline Interview (51 Questions)

Baseline

Patient Follow-Up Interview (34 Questions)

1. 3 Months from Baseline Visit
2. 6 Months from Baseline Visit
3. 12 Months from Baseline Visit
4. 24 Months from Baseline Visit

Patient Interview - During Chemotherapy/Radiation Treatment (11 Questions)

In addition to the above forms, each patient will complete the **Patient Interview During Chemo/Radiation Treatment** as well according to the following schedule:

Within one week prior to the start of each chemotherapy regimen for patients undergoing chemotherapy or every four weeks of RT for patients undergoing radiation therapy alone

Sexual Function Survey (16 Questions)

1. Baseline
2. Within one week prior to the start of each chemotherapy regimen for patients undergoing chemotherapy or every four weeks of RT for patients undergoing radiation therapy alone
3. 3 Months from Baseline Visit
4. 6 Months from Baseline Visit
5. 12 Months from Baseline Visit
6. 24 Months from Baseline Visit

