8.4 Accrual Goal and Accrual Period

To help safeguard 10 enrolling sites per intervention group (as originally proposed), we have invited more than 20 MU NCORPs/NCORPs to participate in this study (as listed on the cover page of the protocol). To further help accrual, we lowered the age limit to 15 years in Addendum 9 (effective from February 6, 2019). Besides the original participating MU NCORPs/NCORPs, interested pediatric MU NCORPs/NCORPs are allowed to participate in the EROS trial as well.

To have adequate power to detect the difference from 50% to 80% in the primary endpoint, the accrual goal of this study was re-calculated to ensure 149 patients in the intervention arm, assuming 16 sites enrolling patients for this trial (8 to the non-intervention group (Arm A) and the other 8 to the intervention group (Arm B)). Patients from each site will be enrolled into one of the four strata depending on the patient's pregnancy status, sexual activity status, and/or her birth intention. Given some sites accrue much faster than the others, a NCORP accrual cap of 45 patients was implemented per Addendum 8.

As of January 4, 2021, 268 patients from 9 Arm A sites and 138 patients from 8 Arm B sites have had been enrolled to this trial. As this is a comparative study, the trial will continue accrual for both arms until Arm B meets its accrual goal of 149 patients which is projected to take another 5 months. Taking into account the site accrual up to January 4, 2021 and the accrual rate in the past three months (i.e., the last three months of 2020, with the top three accrual sites met the accrual cap of 45 patients and closed accrual to Arm A), the final accrual of this study, thus, is expected to be 425 patients (276 from Arm A and 149 from Arm

Rev. Add11

Rev. Add8
Rev. Add9

B). The mean cluster size is projected to be 25 patients assuming 17 enrolling sites in total (~30 patients per cluster for Arm A and ~18 patients per cluster for Arm B). As suggested by Table 1, this study is equipped with more power if the cluster size is larger than the average of 18-19 patients per cluster and/or if the number of clusters per arm is greater than the stated 8 sites per arm in the sample size calculations. The additional patients and sites in Arm A imply the power of this study will be a little larger than stated (i.e., 85% power) to detect a change from 50% to 80% on the primary endpoint with the projected final accrual of 425 patients.

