8.6 Analysis Plan

8.6.1 Plan for the primary objective
With a cluster randomized design, the generalized estimating equations (GEEs) method will be used to evaluate the intervention effect. The GEEs method can be used to construct an extension of standard logistic regression²⁷. For the primary endpoint, appropriate reproductive health management, a GEE model with an exchangeable correlation structure (i.e., assuming every patient within a cluster is equally correlated with every other patient from that cluster) and registering institution as the cluster variable will be fitted to compare the rates between the intervention group and the no intervention group by combining patients in all strata. The appropriate reproductive health management rate at each time point will be summarized, by arm, with frequency and percentage along with its 95% confidence interval. This rate in the non-intervention arm will indicate whether reproductive health needs are adequately addressed (Hypothesis 1, Section [1.4.1](#)). Whether the intervention can improve reproductive health care (Hypothesis 2, Section [1.4.2](#)) can be determined by comparing this rate between the non-intervention arm and the intervention arm.

The same method will be used to evaluate the intervention effect on contraception usage for Stratum 1 and Stratum 2, separately. Since it is expected that contraception usage will be influenced by the number

of children (0, 1-2, >2), type of treatment (chemo vs. RT vs. surgery vs. combination), and disease stage (nonmetastatic vs. metastatic) as well, these factors will be included in the model as covariates. The contraception usage rate at each time point will be reported with frequency and percentage along with its 95% confidence interval. Similar analysis method will be applied to the proportion of patients with pregnancy by the end of 2 years after baseline visit on the study. The analysis will be applied to patients by stratum for each of these secondary endpoints.

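### Sites know their arm before they refer and recruit patients, yet the primary GEE names no patient covariate; a pre-specified adjusted model is a cheap safeguard

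*Combined protocol and SAP*

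**What the plan says.** **Order of events.** Section 4.1: "Once sites have been selected, they will be randomized to the intervention or non-intervention arm", and then "Each participating institution will be sent a notice confirming the assignment of the intervention or non-intervention arm". Section 5.1 limits intervention training to Arm B sites. Providers join after allocation (section 5.5): "Following site randomization and local IRB approval, a consent form will be given to each provider".

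**Who brings patients in.** Section 5.4: "the primary provider will refer the patient to the study personnel for initial contact". The same section has a site research nurse or CRA work with the physicians to find and recruit patients. Section 5.7.2 adds: "If a patient is eligible to participate in this study and the physician approves, the study is further discussed with the patient". A patient's arm follows from her site (section 5.1): "Upon registration to this study, patients will be assigned to a study arm depending on the institutional assignment".

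**Primary analysis.** Section 8.6.1 specifies a logistic GEE with exchangeable correlation and institution as the cluster, which "will be fitted to compare the rates between the intervention group and the no intervention group by combining patients in all strata". It names no patient covariate. The next paragraph of that section, on contraception use, adds number of children, type of treatment and disease stage because they are expected to influence that outcome.

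**Expected predictors.** Hypothesis 1.4.4 and secondary Objective 3 (sections 2.2.3 and 8.6.2) expect clinical and demographic factors to predict adequacy of reproductive health management.

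**Design.** The introduction to section 8 says that matched-pair randomisation was abandoned for a parallel design.

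**The concern.** When individuals are randomised with concealment, nobody can choose patients according to arm. Here allocation is public at the site before any patient is approached, so the mix of recruits could come to differ between arms after randomisation. The sections on recruitment describe no consecutive-referral rule and no recruiter unaware of the arm.

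If the mix did differ on something that predicts appropriate management, a model with arm as its only stated term would attribute the difference to the intervention. The protocol itself expects such predictors. Chance imbalance in patient mix is a second reason to adjust: there are only 17 enrolling sites, and the matching that would have balanced site type and region is gone.

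**Working it through.** **1. The plan's power figure.** Inputs from section 8.3: 50% versus 80%, 8 sites per arm, mean of 15 eligible patients per site, CV 0.8, ICC 0.10, two-sided alpha 0.10, t distribution.

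- Design effect = 1 + ((CV² + 1)m − 1) × ICC = 1 + (1.64 × 15 − 1) × 0.10 = 3.36.
- SE = √[(0.5×0.5 + 0.8×0.2) × 3.36 / 120] = 0.107.
- Non-central t with 14 df: power 0.845, against the stated 0.85. At ICC 0.05 and 0.15 the formula gives 0.951 and 0.741 (stated 0.95 and 0.75).
- Inflation: 120 / (0.95 × 0.85) = 148.6, so 149 per arm and 298 in total, as stated.

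The sample-size arithmetic is not in question. The issue is possible bias.

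**2. What a recruitment-induced difference would do.** The documents give no size for it, so δ is an assumption. Keep the setting of step 1, set the true effect to zero, and put the rates at 50% in Arm A and 50% + δ in Arm B. For δ = 10 points, SE = √[(0.25 + 0.24) × 3.36 / 120] = 0.117. The projected column uses 276 patients at 9 sites and 149 at 8 (section 8.4), each multiplied by 0.95 × 0.85 = 0.8075, which gives about 24.8 and 15.0 evaluable patients per site.

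| Assumed δ (points) | Significant in favour of Arm B, 8 × 15 | Same, projected accrual |
|---|---|---|
| 0 | 5.0% | 5.0% |
| 5 | 10.7% | 11.2% |
| 10 | 20.3% | 21.7% |
| 15 | 34.1% | 36.9% |
| 20 | 51.3% | 55.6% |

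A δ of 10 points would arise if Arm B recruited 20 points more of a patient type whose success rate is 50 points higher (0.20 × 0.50 = 0.10). With a 30-point gap in success rate, the same shift gives 6 points.

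**3. What adjustment does.** A GEE simulation of that 10-point case used 400 trials, 8 sites per arm, mean size 15, CV 0.8 and no arm effect. False positives favouring Arm B were 22.8% unadjusted and 5.0% with the patient type in the model. With a 30-point shift they were 35.8% and 3.3%. This assumes that the characteristic driving recruitment is recorded and modelled.

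A separate simulation (500 trials, 17 sites, trait share 70% versus 50%) made the trait unrelated to the covariates in the model. Rejection was 24% unadjusted and 26% adjusted, so adjustment gave no benefit.

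**4. Does enrolment show that selection occurred?** Section 8.4 reports that "268 patients from 9 Arm A sites and 138 patients from 8 Arm B sites have had been enrolled to this trial": 268/9 = 29.8 and 138/8 = 17.3 per site, a ratio of 1.73.

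- Section 8.3 gives 23.9 and 18.6 for the CV of 0.78. Since 406/17 = 23.9 is the mean, 18.6 is the SD across sites.
- Total sum of squares: 16 × 18.6² = 5,535. Between arms: 9 × 5.90² + 8 × 6.63² ≈ 665. Within-arm SD: √[(5,535 − 665)/15] ≈ 18.0.
- t = 12.5 / (18.0 × √(1/9 + 1/8)) ≈ 1.43 on 15 df, p about 0.17.
- Section 8.4 says that the top three sites reached the 45-patient cap, closing accrual in Arm A. If each enrolled exactly 45 (an assumption), the other six Arm A sites average (268 − 135)/6 = 22.2, and the ratio falls to 1.28.

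The difference is compatible with ordinary variation in site size.

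**The case against.** **Selective recruitment has not been shown.** A reader might infer from the 66%/34% split that Arm B clinicians were choosing their patients. Step 4 shows that the documents do not support this. Section 8.3 also says that recent accrual is closer to equal because of the caps. This part of the objection stands in full: the point concerns exposure to a risk.

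**The referring clinician may not deliver the intervention.** A reader might infer that in Arm B the same provider refers and intervenes. Section 6.1 lists the Reproductive Health Assessment among forms for clinical staff, but that list also holds the abstraction forms, which section 5.7.1 gives to study staff. The intervention content is in Addendum I, which is not among the documents reviewed. The inference is not established, and the point does not need it: it is enough that the site knows its arm.

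**Referral may be routine.** Section 5.4 states no discretion in referral and requires each patient to be enrolled or logged. But Appendix II is for patients who were asked and declined, so it would not capture an eligible patient who was never referred, and section 5.7.2 makes physician approval a condition. The documents do not settle how much room for choice exists.

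**The statistical analysis plan in Addendum II was not available.** It may name covariates. However, section 8.1 cites it for endpoint details, and section 8.6.1 itself sets out the primary model. If the addendum does name covariates, the two should be brought into line.

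**Adjustment may miss the mechanism.** If Arm B recruited patients who were more motivated or clearer about their goals, age, children, stage and cancer type would not capture that. This stands, and it limits what the fix can claim.

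**Conclusion.** The point holds as a cheap improvement. Allocation is known before recruitment, and section 8.6.1 as written leaves the primary comparison without any patient covariate, although the protocol expects patient factors to predict this outcome and adjusts for such factors in a secondary model.

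Whether recruitment differed in kind, in which direction and by how much is unknown. The false-positive figures of about 11% to 51% are conditional on assumed differences of 5 to 20 points and are not estimates for this trial.

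A reader might go further and conclude that the primary result will be biased, or that adjustment would cure it. The documents support neither. Adjustment removes only imbalance carried by the recorded characteristics, whether it came from recruitment or from chance among 17 sites.

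**What to change.** In section 8.6.1, and in Addendum II if it does not already do so:

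- Pre-specify the primary GEE with arm plus a short list of characteristics that are fixed before the provider visit and already collected: age, number of children, disease stage and grouped cancer type. Birth date is taken at registration (section 4.5.3), children and stage are already covariates in section 8.6.1, and analysis by disease site is foreseen in section 1.5. Treatment type is left out because it need not be settled before that visit.
- Report the standardised difference in rates between arms as the primary estimate, and keep the unadjusted GEE as a supporting analysis.
- Tabulate these characteristics by arm.
- State residual recruitment bias as a limitation.

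Date the change before anyone choosing the covariates sees outcomes by arm.

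The cost is a few lines of plan wording and code, with no new data. The downsides are a few patients with missing covariates, and no correction for unrecorded differences such as motivation or clarity of goals. The list should stay short, given 17 sites.
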